# Section F: Design/Procedure

## F1. Design

Select one category that most adequately describes your research:

c) Pilot

Discuss the research design including but not limited to such issues as: probability of group assignment, potential for subject to be randomized to placebo group, use of control subjects, etc.

Thirty four (n=50) patients with diabetes (age 18 years or older) with non-infected deep wounds (grades 2 in the Wagner Ulcer classification) will be randomized into two groups, 17 subjects per group each. The group one will be treated by Meshed DermaCELL and group two will be treated by Meshed Integra template.

The primary outcomes are time to granulation, successful granulation at 8 weeks, and number of failures (e.g. amputation, infection, rejection, re-application) within 8 weeks. Secondary outcomes include time to apply, weekly speed of wound healing after successful granulation and transition to standard wound therapy, success of wound healing at 12 weeks and @16 weeks, cost of wound treatment upto 16weeks (based on patient electronic record), tissue biomechanics after wound healing (e.g. presence of scarring or tissue biomechanics properties leading to increase in shear or pressure post healing), change in skin perfusion (assessed with SPP), change in thermography response, recurrence of ulcers up to 6 months post healing, and other patient centered outcomes including perception of pain, physiological stress response as surrogate of pain (e.g. heart rate variability during dressing change), sleep quality (assessed by PSQI and sensor-based sleep quality index), wound smelling (assessed by Likert scale), and patient perception of benefit (assessed by technology acceptance model, TAM based on perception of benefit and attribute of benefits).

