Device Acceptability Questionnaire: The subject will be handed a questionnaire to evaluate the study device and provide feedback to the research team. We will be asking about level of satisfaction with the product. These may be questions about the time spent to apply the product, the level of comfort, appearance of the product, the appearance of the healed wound (e.g. presence of scarring), ease of walking or standing with the product and after healing, etc.

Matrix Application: During the subject's wound treatment (either in OR or outpatient clinic), the physician will apply the dermal matrix from the group they were placed. The researchers will write down the duration needed for full application of the product. For accurate estimation of time needed for preparation and application, the whole process may be video-recorded for offline estimate of each time.

Vascular Assessment: We will assess perfusion of the macro-circulation with arterial Doppler studies and micro-circulation with Skin Perfusion Pressure measurements. Ankle Brachial Index (ABI) will be measured on both extremities. We will also use the SensiLase system (Väsamed) to measure Skin Perfusion Pressure (SPP) in mmHg. Additionally, we may use the LUNA or SPY Device for Indocyanine Green Fluorescence Imaging. For this purpose a fluorescent agent may be injected into the subject's body to allow us observe the blood circulation to the wound. Indocyanine Green Fluorescence Imaging (SPY or Luna) may be performed based on the medical judgment of the physician. Highly qualified medical/clinical staff will perform this measurement. If so, measurement will take place only during baseline and treatment day.

Wound Photo: At every visit, the Medical/Researcher using a standard digital camera will take a digital photo of the wound. We will ask the subject's permission to take photos/video.

Wound Assessment: Evaluations will be based on data collected from wound assessments and photographs. We use acetate tracings and digital photos. Additionally, we will use thermal imaging to track inflammation.

Thermal Image: A thermal camera will be used to obtain an image of the wound and observe swelling.

Wifi Wound Classification: Podiatrist or vascular surgeon will evaluate the health and wellness of the subject's feet in compliance of standard of care

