The description of every visit is below. Screening/Baseline Visit \*duration of visit 90 minutes This visit will take place at Baylor St. Lukes Medical Center during your surgery day. The researchers will perform as described above: Medical History, Questionnaires (Pain, Social Factors, and Quality of Life, Sleep Quality, Cognitive Assessment, Frailty), Matrix application, Upper Extremity Test, Peripheral Neuropathy, Thermal Image, Vascular Assessment, Wound Assessment, Wifi Wound Classification, and Wound photo.

Visit 1, One Week Later \*duration 50 minutes This visit will take place at Baylor Clinic for a regular follow up appointment. The researchers will perform as described above: Pain Questionnaire, Adverse Event Reporting, Dressing Change, Wound Photo, and Wound Care.

Visit 2, Two Weeks Later \*duration 70 min This visit will take place at Baylor Clinic for a regular follow up appointment. The researchers will perform as described above: Adverse Event Reporting, Wound Assessment, Thermal Image, Dressing Change, Wound Photo, and Wound Care.

Visit 3, Three Weeks Later \*duration 50 min This visit will take place at Baylor Clinic for a regular follow up appointment. The researchers will perform as described above: Adverse Event Reporting, Dressing Change, Wound Photo, and Wound Care.

Visit 4, Four Weeks Later \*duration 70 min This visit will take place at Baylor Clinic for a regular follow up appointment.

The researchers will perform as described above: Pain Questionnaire, Adverse Event Reporting, Sleep Quality Questionnaire, Wound Assessment, Dressing Change, Wound Photo, Thermal Image, and Wound Care.

Visit 5, Five Weeks Later \*duration 70 min This visit will take place at Baylor Clinic for a regular follow up appointment. The researchers will perform as described above: Adverse Event Reporting, Dressing Change, Wound Photo, Granulation Assessment, and Wound Care.

Visit 6, Six Weeks Later \*duration 70 min This visit will take place at Baylor Clinic for a regular follow up appointment. The researchers will perform as described above: Adverse Event Reporting, Dressing Change, Thermal Image, Wound Photo, Granulation Assessment, and Wound Care.

Visit 7, Seven Weeks Later \*duration 70 min This visit will take place at Baylor Clinic for a regular follow up appointment. The researchers will perform as described above: Adverse Event Reporting, Dressing Change, Wound Photo, Granulation Assessment, and Wound Care.

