Visit 16, Sixteen Weeks Later \*duration 90 min This visit will take place at Baylor Clinic for a regular follow up appointment. The researchers will perform as described above: Pain Questionnaire, Sleep Quality Questionnaire, Device Acceptability Questionnaire, Adverse Event Reporting, Dressing Change, Wound Photo, Thermal Image, Wound Assessment, Vascular Assessment, Granulation Assessment, Wound Care, Wifi Wound Classification, Upper Extremity Assessment.

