## G2. Data Analysis

Provide a description of your plan for data analysis. State the types of comparisons you plan (e.g. comparison of means, comparison of proportions, regressions, analysis of variance). Which is the PRIMARY comparison/analysis? How will the analyses proposed relate to the primary purposes of your study?

The primary outcomes are time to granulation, successful granulation at 8 weeks, and number of failures (e.g. amputation, infection, rejection, re-application) within 8 weeks. Mixed models accommodate the longitudinal design; allow for testing differences between groups in patterns over time as well as at specific time points; are consistent with an intention to treat analysis (9), and are valid for data which are missing completely at random or at random (10). Number of failures as well as number of recurrence of ulcers over the 6 month follow-up will be modelled with a generalized linear model using an appropriate count outcome (Poisson, zero-inflated Poisson, negative binomial for overdispersion). Rate ratios comparing intervention arms will be estimated from this model. Appropriate mixed models (linear or generalized linear, for noncontinuous outcomes or logistic regression for binary data) will be used to test the intervention effect for each of the secondary outcomes (e.g. tissue biomechanics, mobility, patient centered outcomes, recurrence of ulcers, etc). A Kaplan-Meier survivorship analysis will be used for estimating time to event for none successful healing probability over time by treatment and the p-value will be calculated using the Log-rank (Mantel-Cox) test. Hazard ratios will be used to indicate the probability of closure at any given point in time for Derma-Cell v. Integra treatment. Univariate logistic regression analyses will be performed to delineate predictive factors of successful granulation at 8 weeks, successful wound healing at 12 weeks, and successful wound healing at 16 weeks. Results will be controlled for potential confounding variables including age, sex, BMI, HbA1c, neuropathy severity, vascular status, frailty, mobility status, and initial wound size. The p-values for weekly % wound area and % wound area reduction through 16 weeks will be calculated using t tests. All p-values, for both the categorical and continuous data, will be calculated using a two-sided alpha of 0.05.

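### G2 does not say how the baseline values of pain, PSQI, skin perfusion and thermography enter the mixed models, so available precision on these secondary outcomes is not secured

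*Combined protocol and SAP*

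**What the plan says.** **Baseline.** The Screening/Baseline Visit in F2 includes "Questionnaires (Pain, Social Factors, and Quality of Life, Sleep Quality, Cognitive Assessment, Frailty") and, in the same list, "Peripheral Neuropathy, Thermal Image, Vascular Assessment, Wound Assessment, Wifi Wound Classification, and Wound photo". The vascular assessment includes SPP: "We will also use the SensiLase system (Väsamed) to measure Skin Perfusion Pressure (SPP) in mmHg". F2 names the PSQI as the sleep questionnaire.

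**Follow-up (F2 visit list).** Pain is repeated at weeks 1, 4, 8, 12 and 16, the sleep questionnaire at weeks 4, 8, 12 and 16, and the thermal image every two weeks to week 16. The vascular assessment returns only at week 16, whose list ends with "Thermal Image, Wound Assessment, Vascular Assessment, Granulation Assessment, Wound Care, Wifi Wound Classification, Upper Extremity Assessment".

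**Outcome definitions (F1).** Two of the four are framed as change: "change in skin perfusion (assessed with SPP), change in thermography response". Pain and sleep are not; sleep is given as "sleep quality (assessed by PSQI and sensor-based sleep quality index").

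**Analysis (G2).** Mixed models "will be used to test the intervention effect for each of the secondary outcomes". They are described as testing group differences both in patterns over time and at particular times. After the logistic-regression sentence comes a list of potential confounders: age, sex, BMI, HbA1c, "neuropathy severity, vascular status, frailty, mobility status, and initial wound size". G2 mentions neither an outcome's own baseline value nor a common baseline mean.

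**The concern.** When an outcome is measured before and after treatment, three analyses of a randomised comparison are in common use: compare follow-up values, compare changes, or compare follow-up values adjusted for baseline. All three estimate the same effect without bias on average. Their variances differ, and for equal variances over time and a correlation between 0 and 1 the adjusted analysis has the smallest.

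This matters more than usual here. Section G1 sets the sample size on application time alone and hopes only to see a trend in other outcomes. Pain, sleep, perfusion and thermography were therefore never powered. Section D suggests that patient-centred outcomes may differ between the products, and names pain and sleep. With 17 to 25 patients per arm, chance baseline differences are also sizeable, and the unadjusted analyses either ignore them or, as change scores, over-correct them. Leaving the choice open also allows it to be made after the data are seen.

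**Working it through.** **1. The plan's own figure.** G1 assumes 3±2 against 5±2 minutes, so d = (5 − 3)/2 = 1, with two-sided alpha 0.05 and power 80%. The noncentral t gives 17 per group (power 80.7%; 16 per group gives 78.1%). The stated 17 reproduces. It concerns application time, which has no baseline. F1 and G1 give both 34 and 50 as the total, so 17 and 25 per arm are both used below.

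**2. What the planned model estimates.** Suppose baseline is one of the responses and the arm-by-visit means are free. With complete data, the arm contrast at a given visit is the follow-up-only difference, and the arm-by-time contrast from baseline is the difference in change. The gain from adjustment appears only if baseline is a covariate or if the arms share one baseline mean. G2 states neither.

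**3. Variance, single follow-up visit.** Let r be the baseline-to-follow-up correlation, with equal variance at both times. The documents do not give r; 0.3 to 0.7 is assumed. Relative to follow-up only (1), the factors are 2(1 − r) for the change score and 1 − r² for the adjusted comparison.

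| r | Change score | Adjusted | Adjusted ÷ change |
|---|---|---|---|
| 0.3 | 1.40 | 0.91 | 0.65 |
| 0.5 | 1.00 | 0.75 | 0.75 |
| 0.7 | 0.60 | 0.51 | 0.85 |

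The adjusted variance is thus 91%, 75% or 51% of follow-up only, equivalent to 1.10, 1.33 or 1.96 times the patients. At r = 0.3 the change score is worse than ignoring baseline.

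**4. Power, single follow-up visit.** Noncentral t, 2n − 2 degrees of freedom (2n − 3 when adjusted). The true effect of 0.8 SD is an assumption for illustration.

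| n per arm | r | Follow-up only | Change score | Adjusted |
|---|---|---|---|---|
| 17 | 0.3 | 62% | 48% | 66% |
| 17 | 0.5 | 62% | 62% | 74% |
| 17 | 0.7 | 62% | 83% | 89% |
| 25 | 0.3 | 79% | 65% | 83% |
| 25 | 0.5 | 79% | 79% | 89% |
| 25 | 0.7 | 79% | 95% | 97% |

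The effect detectable with 80% power at 17 per arm falls from 0.99 SD (follow-up only) to 0.95, 0.86 or 0.71 SD at r = 0.3, 0.5 or 0.7. At 25 per arm it falls from 0.81 to 0.77, 0.70 or 0.58 SD.

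**5. Chance imbalance.** The difference in baseline means has SD √(2/17) = 0.34 SD units at 17 per arm and √(2/25) = 0.28 at 25 per arm.

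**6. Pooled visits.** SPP has only one follow-up, so step 3 fits it directly. PSQI has four. If all visits are equally correlated at r, the mean of four follow-ups has variance (1 + 3r)/4 for follow-up only, that plus 1 − 2r for change, and that minus r² when adjusted.

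| r | Follow-up only | Change | Adjusted | Adjusted ÷ follow-up only |
|---|---|---|---|---|
| 0.3 | 0.475 | 0.875 | 0.385 | 81% |
| 0.5 | 0.625 | 0.625 | 0.375 | 60% |
| 0.7 | 0.775 | 0.375 | 0.285 | 37% |

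The gain differs from the single-visit figure but does not vanish.

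**The case against.** The strongest reply is that the plan is silent on baseline and is not shown to discard it. A longitudinal mixed model with baseline among the responses and a common baseline mean would recover about the same precision. The covariate list is introduced as including certain variables, so it is open. It contains initial wound size, so adjusting for a starting value is not foreign to the plan, and vascular status may carry baseline SPP. The list follows the logistic-regression sentence and may not govern the mixed models at all. This stands as far as it goes: a reader might infer that the trial throws its baseline data away, and the documents do not show that. It does not remove the point, because the precision depends on a term or a constraint that G2 does not state.

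Three other inferences are tempting and should not be drawn:
- **That differences are expected on all four outcomes.** Section D names pain, sleep and smell among patient-centred outcomes, and speaks only of possible differences. Perfusion and thermography are not named there. For those two, baseline already enters through the change definition, and the issue is only adjustment against change.
- **That baseline adjustment is the largest gain available without more patients.** Under equal correlation, averaging the five pain follow-ups gives a factor (1 + 4r)/5 = 0.44, 0.60 or 0.76 at r = 0.3, 0.5 or 0.7, against 0.91, 0.75 or 0.51 for single-visit adjustment. Averaging gains more at 0.3 and 0.5.
- **That the power figures above describe the planned model.** They are for single-visit comparisons, with r and the effect size assumed.

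It is also fair to say that F1 classes the study as a pilot and that these are a few of many secondary outcomes. That limits the weight of the point. Finally, F2 places baseline on the day of surgery, in the same visit as matrix application, and gives no order. A value taken after application would not be a valid baseline covariate.

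**Conclusion.** The point holds as a gap in specification with a better method readily available. All four measures are collected at baseline and again later, and G2 does not put an outcome's own baseline into the model; the omission is clearest for pain and PSQI. On a single follow-up visit, adjustment removes 9% to 49% of the follow-up-only variance and 15% to 35% of the change-score variance. The range rests on an assumed correlation of 0.3 to 0.7 and equal variances over time. At the low end the gain over follow-up only is small (62% to 66% power for 0.8 SD at 17 per arm). Randomisation protects against bias on average, so this is a matter of precision and prespecification for secondary outcomes. The primary outcomes are unaffected.

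**What to change.** Add to G2: for pain, PSQI, SPP and thermography, the mixed model includes that outcome's own pre-application value as a covariate (or includes baseline as a response with arm means constrained to be equal there), and the arm effect is reported as the adjusted difference at a stated visit. Week 16 is one candidate, being the only follow-up visit at which all four are measured. Analyse the two outcomes that F1 frames as change in the same way, not as raw change.

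State in F2 that these four baseline measures are taken before matrix application.

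The cost is wording and one degree of freedom per model, with no new data. If any of the four is now taken after application, the order of that measurement would also have to change before it could serve as a baseline covariate.

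### The healing p-value comes from a log-rank test with no covariates, and the plan does not say whether its adjustment for initial wound size reaches that comparison or which result counts

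*Combined protocol and SAP*

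**What the plan says.** G2 (Data Analysis) plans a Kaplan-Meier analysis of healing by treatment, for which "the p-value will be calculated using the Log-rank (Mantel-Cox) test". The next sentence gives the effect measure: "Hazard ratios will be used to indicate the probability of closure at any given point in time for Derma-Cell v. Integra treatment". Neither sentence names strata, covariates or a regression model.

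The paragraph then turns to prediction ("Univariate logistic regression analyses will be performed to delineate predictive factors of successful granulation at 8 weeks", and healing at 12 and 16 weeks). Directly after that it says: "Results will be controlled for potential confounding variables including age, sex, BMI, HbA1c, neuropathy severity, vascular status, frailty, mobility status, and initial wound size". It does not say which results are meant. All p-values "will be calculated using a two-sided alpha of 0.05".

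Wound size is available at baseline. Under Wound Assessment, F2 (Procedure) says "We use acetate tracings and digital photos", and that assessment is listed at the Screening/Baseline visit. F1 (Design) describes randomisation into two groups and mentions no stratification. The eligibility criteria set no limits on wound area.

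F1 classes the study as a pilot. Its primary outcomes concern granulation and failures; healing at 12 and 16 weeks is secondary. Section D, however, lists healing time among the wound outcomes under the primary objective.

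**The concern.** The only p-value named for healing uses no baseline information, although the plan itself regards wound size as a possible confounder and measures it. Three things follow.

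- **Ambiguity.** If the adjustment sentence covers only the logistic models, the healing comparison is unadjusted. If it covers everything, there will be an unadjusted p-value beside an adjusted hazard ratio from an unnamed model, with no rule on which one counts. That choice would be made after the data are seen.
- **Power.** If larger wounds heal more slowly, a test that ignores size has less power than one that uses it.
- **Chance imbalance.** With 17 or 25 patients per arm, one arm can end up with clearly larger wounds, and the unadjusted test cannot separate that from a product effect. G1 says observed trends may prompt a further trial or a larger sample, so a trend produced by wound size could misdirect that decision.

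**Working it through.** **1. The plan's own figure.** G1 sizes the trial on application time: 3 v 5 min, SD 2, two-sided 5%, power 80%. The normal approximation gives n = 2(1.960 + 0.842)²(2/2)² = 15.7, so 16 per arm. The exact t-test gives 16.7, so 17, with 80.7% power. The stated 17 per group reproduces, but it says nothing about healing. F1 gives the total as both 34 and 50, so 17 and 25 per arm are both used below.

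**2. Simulation set-up.** The documents give no healing rate, hazard ratio (HR) or prognostic strength of wound size, so these are assumptions. Hazard = λ·exp[ln(HR)·treatment − b·x], where x is standardised log baseline area and b is the log-HR per SD. λ is set so that 50% of controls heal by 16 weeks; there is no dropout; 2,500 trials per cell. The log-rank test (|z| > 1.96) is compared with the Wald test for treatment from a Cox model containing treatment and x. Runs at 60% control healing used weekly visits and 1,200 trials per cell. Monte Carlo error is at most √(0.25/2,500) = 1.0 point and √(0.25/1,200) = 1.4 points respectively.

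Check: the Schoenfeld formula, power = Φ(√d·ln(HR)/2 − 1.96), with d = 34 and HR 2.5 gives Φ(5.83 × 0.916/2 − 1.96) = Φ(0.71) = 76%. The simulated log-rank power at b = 0 was 75%, with 33.1 events on average.

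**3. Power (%), log-rank v adjusted Cox**

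| Assumptions | b = 0 | 0.3 | 0.5 | 0.8 | 1.0 |
|---|---|---|---|---|---|
| HR 2.5, 50%, 17/arm | 57.9 v 56.0 | 54.1 v 54.4 | 48.6 v 53.9 | 38.6 v 52.1 | 33.9 v 51.2 |
| HR 2.5, 50%, 25/arm | 75.0 v 73.8 | 71.1 v 72.9 | 63.9 v 71.3 | 53.4 v 68.1 | 46.0 v 67.3 |
| HR 2.5, 50%, 25/arm, further run | 74 v 72 | – | 59 v 67 | 50 v 66 | – |
| HR 2.5, 60%, 17/arm | – | – | 52 v 54 | 40 v 51 | – |
| HR 2.5, 60%, 25/arm | 79 v 76 | – | 70 v 74 | 55 v 70 | – |
| HR 2, 50%, 17/arm | 35.6 v 34.3 | 34.0 v 32.9 | 29.7 v 33.2 | 23.7 v 32.4 | 20.2 v 29.7 |
| HR 2, 50%, 25/arm | 49.2 v 47.3 | 44.6 v 46.9 | 41.6 v 46.5 | 34.0 v 44.4 | 28.8 v 45.2 |

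The log-rank test gains 1 to 3 points at b = 0 and is within about 2 points either way at 0.3. It loses 2 to 8 points at 0.5. At 0.8 it loses 9 to 16 points (11 to 16 at HR 2.5, 9 to 10 at HR 2).

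**4. Type I error over all randomisations (HR 1).** Log-rank 4.5% to 6.2%; adjusted Cox 4.4% to 5.6%.

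**5. Chance imbalance.** The difference in mean x between arms has standard error √(2/m).
- m = 17: 0.343, so P(|difference| > 0.5 SD) = 2[1 − Φ(0.5/0.343)] = 14.5%.
- m = 25: 0.283, so 2[1 − Φ(0.5/0.283)] = 7.7%.

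Within those trials, at HR 1 and 50% control healing, the log-rank test rejected in 5% to 7% (b = 0 to 0.3), 9% to 11% (0.5), 11% to 15% (0.8) and 14% to 18% (1.0). The 60% runs gave 12% to 18% at 0.8. These cells are small: 7.7% of 2,500 is about 193 trials, so a rate of 15% has a standard error of about 2.6 points.

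**6. All nine covariates.** The 50% runs averaged 17 to 33 events, so 17/9 = 1.9 to 33/9 = 3.7 events per listed covariate. That is too few for a stable model.

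**The case against.** The strongest reply is that the plan already adjusts. The adjustment sentence refers to results without restriction. The analyses just before it are univariate, so limiting it to them is strained. Hazard ratios usually come from a Cox model, which can carry wound size. This stands in part: a reader might infer that wound size is ignored altogether, and the documents do not support that. What remains is that the named p-value is not adjusted, the model is not named, and precedence is not stated.

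Other stronger readings also fail.

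- **That the test is invalid.** Step 4 shows otherwise. The excess false positives arise only given an imbalanced allocation.
- **That serious imbalance is likely.** Imbalance above 0.5 SD is a minority event.
- **That a log-rank test can never adjust.** A stratified one can. That this one is unstratified is read from the plan's silence.
- **That the hazard ratio is biased.** At a true adjusted HR of 2.5 and b = 0.8, the median unadjusted HR was 1.95. This is largely non-collapsibility: the two are different quantities.

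Section D assumes that wound outcomes are comparable between products, so power at HR 2.5 is not what the trial set out to secure. That is fair. If the products are truly equivalent, there is no power to recover, and the case rests on the ambiguity and on protection against imbalance.

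**Conclusion.** The concern holds as an unresolved choice with a conditional cost. The healing p-value is fixed as a log-rank test without stated strata or covariates, while the adjusted analysis has no model, no clear scope and no stated standing.

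The power cost depends on how strongly wound area predicts healing, which the documents do not give. It is negligible for a weak relation and material for a strong one. The gains assume proportional hazards, a hazard ratio of 2 to 2.5 and 50% to 60% of controls healed by 16 weeks; other values would change them. The trade is lopsided in favour of adjustment: a small loss if area is irrelevant, against a gain several times larger if it matters.

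Severity is minor to moderate. The primary outcomes in F1 are not affected, and G1 seeks only trends in outcomes other than application time.

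**What to change.** In G2, replace the source of the healing result with wording such as:

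*The treatment comparison for time to healing (hazard ratio, 95% confidence interval and p-value) will come from a Cox model with treatment and log baseline wound area, using the tracing from the Screening/Baseline visit. Kaplan-Meier curves and the log-rank test will be shown as supportive. Adjustment for the other eight listed variables is confined to exploratory or sensitivity analyses.*

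A log-rank test stratified by wound size would be an alternative. Whichever is chosen must be named before outcome data are examined.

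The cost is a few sentences and no new data. There are two downsides: 1 to 3 points of power lost if wound area proves unrelated to healing, and an adjusted hazard ratio that is conditional on wound area and so will differ from the unadjusted one. The report should label which is which.

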# Section G: Sample Size/Data Analysis

#### G1. Sample Size

How many subjects (or specimens, or charts) will be used in this study? Local: 50 Worldwide: 50

Please indicate why you chose the sample size proposed:

There is no prior studies to report the major primary outcomes for comparison between DermaCELL and Integra. Based on interviewing our podiatrist who worked with both Integra and DermaCELL, we estimated the time needed to apply each matrices in the OR. We hypothesized that time needed to apply DermallCELL is approximately 3±2 min while the time needed to apply Integra is estimated to be 5±2min (Cohen¿s effect size d=1). Assuming an alpha of 5% and power of 80% and two tailed t-test comparison, 17 subjects per group needed to be recruited to observe a significant difference between two groups from point of view of application time. We anticipate that this sample size should be also sufficient to observe noticeable trend in other outcomes. Based on results of this study, another RCT may be addressed to clinically validate the

observed noticeable trends. Alternatively, the sample size may be increased upon available of budget, approval of sponsor, and noticeable observed trend based on the first 20 recruited subjects (ten per group).

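### Predictive factors for granulation and healing are to be named from univariate logistic tests at an unadjusted 0.05, with no candidate list, no exploratory label and no link to the stated covariate adjustment

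*Combined protocol and SAP*

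**What the plan says.** All of this stands in one paragraph, section G2 (Data Analysis) of the combined protocol and SAP.

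- **Method.** "Univariate logistic regression analyses will be performed to delineate predictive factors of successful granulation at 8 weeks". The sentence goes on to two more endpoints, so the screen covers "predictive factors of successful granulation at 8 weeks, successful wound healing at 12 weeks, and successful wound healing at 16 weeks".
- **Adjustment.** The next sentence reads: "Results will be controlled for potential confounding variables including age, sex, BMI, HbA1c, neuropathy severity, vascular status, frailty, mobility status, and initial wound size".
- **Threshold.** The paragraph closes with "All p-values, for both the categorical and continuous data, will be calculated using a two-sided alpha of 0.05".

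G2 does not list the factors to be screened. The nine named variables are introduced as confounders, and the word introducing them leaves the list open. G2 states no handling of multiplicity and does not call the analysis exploratory. Elsewhere, F1 classes the study as a pilot, and G1 says that a further randomised trial may follow to validate observed trends.

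**The concern.** Testing factors one at a time on three endpoints, each at 0.05, and naming those that pass will often produce a named factor when none matters. The wording of G2 invites the report to call such a factor predictive, and nothing in the paragraph tells the reader to discount it.

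The adjustment sentence adds a second difficulty. A univariate model has one factor in it. If results are also controlled for nine variables, an analyst cannot tell whether the one-factor result, an adjusted result or both decide that a factor is predictive. With 34 or 50 patients these routes can disagree, and the choice would be open after the data are seen.

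At stake is the credibility of the predictor findings and of any follow-on trial that used them, for example to choose its population or stratification factors.

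**Working it through.** **The plan's own figures.** The documents state no false-positive rate for this analysis, so there is none to reproduce. The only sizing in G1 is for application time: "time needed to apply DermallCELL is approximately 3±2 min while the time needed to apply Integra is estimated to be 5±2min", a difference of 2 with SD 2, so d = 1. At two-sided 5% and 80% power the t-test solution is 16.7 per group, rounded up to 17, with 80.7% power at 17. That agrees with G1, but it says nothing about predictor analyses. The total is 34 on that basis (2 × 17), while G1 also gives "Local: 50 Worldwide: 50"; both sizes are used below.

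**Inputs**

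- Endpoints: 3 (G2).
- Level per test: 0.05, two-sided, unadjusted (G2).
- Candidate factors: not stated. Nine is an assumption, taken from the confounder list in G2.
- True state: every candidate unrelated to every endpoint (assumption).

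**Arithmetic.** With m independent tests of null factors, P(at least one p<0.05) = 1 − 0.95^m.

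- Three fully redundant endpoints, so m = 9: 1 − 0.95^9 = 37.0%.
- All tests independent, so m = 9 × 3 = 27: 1 − 0.95^27 = 75.0%.
- Expected false positives over 27 tests: 27 × 0.05 = 1.35. This expectation does not need independence.

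**Sensitivity to the candidate count** (three endpoints, independent tests):

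| Null candidates | Tests | P(at least one) |
|---|---|---|
| 3 | 9 | 37.0% |
| 5 | 15 | 53.7% |
| 6 | 18 | 60% |
| 7 | 21 | 65.9% |
| 9 | 27 | 75.0% |
| 15 | 45 | 90.1% |

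The row for 6 also describes nine candidates of which three are truly prognostic (9 − 3 = 6). The row for 5 describes nine of which four are.

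**Dependence and choice of test.** Univariate logistic fits were simulated with nine null factors, 2,500 runs per setting. The endpoint rates (70%, 40%, 60%) and the correlations are assumptions. Except in the first setting, healing at week 12 implies healing at week 16.

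| Setting | N | Wald | Likelihood ratio |
|---|---|---|---|
| Independent endpoints, uncorrelated factors | 34 | 65.0% | 80.6% |
| | 50 | 69.9% | 80.2% |
| Granulation–healing correlation 0.5, uncorrelated factors | 34 | 58.5% | 75.0% |
| | 50 | 63.4% | 74.0% |
| Correlation 0.8, uncorrelated factors | 34 | 58.6% | 74.8% |
| | 50 | 61.1% | 71.7% |
| Correlation 0.8, factors correlated 0.3 | 34 | 53.4% | 70.3% |
| | 50 | 57.7% | 68.2% |

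In the first setting the closed form gives 75.0%. At these sample sizes the Wald test falls below that and the likelihood-ratio test above it. The choice of test alone moves the answer by about 10 to 17 percentage points, and G2 does not name the test. A second simulation (4,000 runs, same endpoint rates) gave 71–72% for score tests with uncorrelated factors, and 47–51% for Wald tests with factors correlated 0.5.

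**The two sentences side by side.** The adjustment sentence can be read in three ways. It may refer to the treatment models earlier in the paragraph, leaving the predictor models univariate. It may describe an adjusted step after the univariate one. Or it may mean that each factor is adjusted for the others, in which case the models are not univariate. G2 does not say which, nor which result decides.

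**The case against.** **The size is not in the plan.** A reader might infer that a fixed false-positive probability, such as 70%, is built into the analysis. The documents do not support that. The figure needs nine confounders from an open list to be the candidates, all of them null and mutually uncorrelated, and a score or likelihood-ratio test. The list includes initial wound size, vascular status and HbA1c, some of which may well be prognostic. This objection stands, and it is why a conditional range is given. It does not rescue the rule: three null candidates on three independent endpoints already give 37%. The candidate list could also exceed nine, since F2 collects many other baseline variables.

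**The exploratory status can be inferred.** The study is a pilot, predictor identification is neither an objective (section D) nor a listed outcome (F1), and G1 looks only for trends in outcomes other than application time. This largely stands and limits the severity. But the threshold in G2 is stated for all p-values, and its verb for these models is to delineate predictive factors. The context is never carried into the rule.

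**Univariate and controlled need not conflict.** A reader might infer a flat contradiction. The three readings above show an ambiguity instead. That point stands; the need to settle the reading remains.

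**Exaggerated estimates.** Factors selected on p<0.05 in a small sample tend to be overestimated. That follows from the selection and holds for multivariable models too, so it is no special charge against univariate ones. It is a reason to report every factor examined with an interval.

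**Conclusion.** The point holds as a minor one. G2 sets a rule under which factors may be called predictive from univariate tests on three endpoints at an unadjusted 0.05, with no candidate list, no exploratory label and no statement of how univariate models relate to the nine-variable adjustment.

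If the nine listed variables were the candidates and all were null, the chance of at least one false predictive factor would be roughly 37% (fully redundant endpoints) to 75% (independent tests). These are reference points, not strict bounds: correlated factors, truly prognostic factors or the Wald test lower the figure, while a longer list or the likelihood-ratio test raises it. On any plausible list it is far above 5%.

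A reader might also infer that the type I error of the DermACELL versus Integra comparison is inflated by this screen. It is not: these tests concern patient factors and do not enter the treatment comparison. Multiplicity among the primary outcomes, and the discrepancy between 34 and 50 patients, are separate matters.

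**What to change.** Replace the univariate-regression sentence in G2 with:

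> Associations of baseline factors with granulation and healing are exploratory. For each endpoint, one Firth-penalised logistic model with treatment and a few baseline factors chosen in advance from the listed variables (for example initial wound size, vascular status and HbA1c) will be fitted, and odds ratios reported with 95% CIs for all factors examined. No factor will be called predictive on p<0.05 alone.

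The final factors should be named before outcome data are seen, since the missing list is part of the gap. The adjustment sentence should also say which models it governs.

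Holm adjustment across factors and endpoints is optional. Over 27 tests its strictest step would be 0.05/27 = 0.00185, and in a pilot side analysis the intervals are more informative.

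Cost: a few sentences of SAP text and minor programming. The downside is that fewer factors will be declared significant.
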